Safety assessments will include the incidence, nature, and severity of adverse events and laboratory abnormalities graded per the National Cancer Institute Common Terminology Criteria for Adverse Events, Version 4.0 (NCI CTCAE v4.0). Laboratory safety assessments will include the regular monitoring of hematology and blood chemistry.

Serum samples will be collected in patients in Arm A (atezolizumab and enzalutamide) to monitor atezolizumab pharmacokinetics and to detect the presence of antibodies to atezolizumab. Plasma samples to monitor enzalutamide and N-desmethyl enzalutamide pharmacokinetics will also be collected in the safety run-in phase and in a PK cohort in the randomized phase (approximately 30 patients per treatment arm). Patient samples, including archival tumor tissues, as well as urine, serum, plasma and whole blood, will be collected for future exploratory biomarker assessments for all patients in the randomized phase.

It is recommended that patients undergo tumor biopsy sample collection, if deemed clinically feasible by the investigator, at the time of first evidence of confirmed radiographic disease progression according to PCWG3 criteria (within 40 days after confirmed radiographic progression or prior to the start of new anti-cancer treatment, whichever is sooner). These samples will be analyzed to evaluate the utility of the biopsy in distinguishing pseudoprogression (caused by tumor-infiltrating ICs) from true progression. In addition, tumor tissue biomarkers related to resistance, disease progression, and clinical benefit of atezolizumab may be analyzed.

Patients who are withdrawn from study treatment will be evaluated within 30 days and approximately 120 days after last study treatment for a treatment discontinuation visit and safety visit, respectively. Thereafter, patients will enter a post-trial access program (as applicable).

An external iDMC will evaluate safety and efficacy data according to policies and procedures detailed in an iDMC Charter (see Section 3.2).

A schedule of activities is provided in [Appendix 1](#).

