## **4.5 STUDY ASSESSMENTS**

The schedule of activities to be performed during the study is provided in [Appendix 1](#). All activities must be performed and documented for each patient. Patients will be closely monitored for safety and tolerability throughout the study. Patients should be assessed for toxicity prior to each dose; dosing will occur only if the clinical assessment and local laboratory test values are acceptable.

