Focal palliative radiography (e.g., external-beam radiotherapy to address single sites of disease), initiation of bisphosphonates or denosumab, standard-of-care corticosteroid use of no greater than the equivalent of 10 mg of prednisone or prednisolone per day, and pain management are allowed and should not result in discontinuation of study treatment. However, patients should be evaluated for clinically apparent SSE.

The primary reason for study treatment discontinuation should be documented on the appropriate eCRF. Patient withdrawal of consent may be a reason for discontinuation of study treatment. Patients enrolled in the safety run-in period who discontinue study treatment without completing the first 21-day treatment cycle may be replaced. All other patients who discontinue study treatment prematurely will not be replaced.

Patients will return to the clinic for a treatment discontinuation visit  $\leq 30$  days after the last dose of study treatment. The visit at which the tumor assessment shows confirmed progressive disease may be used as the treatment discontinuation visit.

After treatment discontinuation, patients will be asked to return to the clinic 120 days  $\pm$  30 days after the last study treatment for a safety visit. Thereafter, patients will enter a post-trial access program.

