#### **5.3.1 Adverse Event Reporting Period**

Investigators will seek information on adverse events at each patient contact. All adverse events, whether reported by the patient or noted by study personnel, will be recorded in the patient's medical record and on the Adverse Event eCRF.

**After informed consent** has been obtained **but prior to initiation of study treatment**, only serious adverse events caused by a protocol-mandated intervention (e.g., invasive procedures such as biopsies, discontinuation of medications) should be reported (see Section 5.4.2 for instructions for reporting serious adverse events).

**After initiation of study treatment**, all adverse events will be reported until 30 days after the last dose of study treatment or until initiation of new systemic anti-cancer therapy, whichever occurs first, and serious adverse events and adverse events of special interest will continue to be reported until 90 days after the last dose of study treatment or until initiation of new systemic anti-cancer therapy, whichever occurs first.

Instructions for reporting adverse events that occur after the adverse event reporting period are provided in Section 5.6.

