#### **6.5                SAFETY ANALYSES**

Safety analyses will be performed on the safety-evaluable population, which is defined as all randomized patients from the global enrollment phase who receive any amount of any component of study treatments. Patients will be summarized according to the treatment actually received. Specifically, for patients randomized to the enzalutamide alone arm, if atezolizumab was received by mistake, patients will be grouped under the atezolizumab arm in the safety analyses.

Exposure to study treatment will be summarized to include treatment duration, number of doses, and dose intensity.

Verbatim description of adverse events will be coded to MedDRA preferred terms and graded according to NCI CTCAE v4.0. All adverse events occurring during or after the first study-drug dose will be summarized by treatment arm and NCI CTCAE grade. In addition, serious adverse events, Grade  $\geq$  3 adverse events, adverse events of special

interest (see Section 5.2.2), adverse events leading to treatment discontinuation, and/or modification will be summarized.

Laboratory abnormalities will be summarized by treatment arm and grade.

Changes in selected vital signs will be summarized by treatment arm.

Deaths and causes of death reported during the study treatment period and those reported during the follow-up period after treatment completion/discontinuation will be summarized by treatment arm.

In addition, safety data will be presented in summary tables split by subgroups defined by age, sex, and race/ethnicity, as well as other potential risk factors as appropriate. Additional details will be provided in the SAP prior to performing the analyses.

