## Appendix 1 Schedule of Activities (cont.)

	Screening a	Treatment (Each Cycle = 21 days)	Treatment Discontinuation (≤ 30 Days) b	Safety Visit c (120 Days ± 30 Days)	Study Termination d
	Days -28 to -1	Day 1 (± 3 Days for Cycles ≥ 2)			
Symptomatic skeletal events w			x		
Atezolizumab infusion x		x			
Enzalutamide treatment y		x			
Adverse events z	x		x		
Survival and anti-cancer therapy follow-up d				x	x

ECOG = Eastern Cooperative Oncology Group; eCRF = electronic Case Report Form; FFPE = formalin fixed paraffin embedded; HBcAb = hepatitis B core antibody; HBsAb = hepatitis B surface antibody; HBsAg = hepatitis B surface antigen; HBV = hepatitis B virus; HCV = hepatitis C virus; IV = intravenous; PCWG3 = Prostate Cancer Working Group 3; PD-L1 = programmed death-ligand 1; RECIST = Response Evaluation Criteria in Solid Tumors; SSE = symptomatic skeletal event; T3 = triiodothyronine; T4 = thyroxine; TSH = thyroid-stimulating hormone.

Notes: Assessments scheduled on the days of study treatment infusions should be performed before the infusion unless otherwise noted.

- a Written informed consent is required for performing any study-specific tests or procedures. Signing of the Informed Consent Form can occur outside the 28-day screening period. Results of standard-of-care tests or examinations performed prior to obtaining informed consent and within 28 days prior to study entry (except where otherwise specified) may be used for screening assessments rather than repeating such tests. If re-screening is required, then HBV, HCV, HIV, and autoantibody testing from the initial screening may be acceptable for screening assessment if performed < 60 days from Cycle 1 Day 1.
- b Patients will be asked to return to the clinic not more than 30 days after the last study treatment for a treatment discontinuation visit.
- c Patients will be asked to return to the clinic 120 days ± 30 days after the last study treatment for a safety visit. Only patients taking atezolizumab are required to return for the safety visit.

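### Footnote c of Appendix 1 requires the 120-day safety visit of atezolizumab patients only, contrary to Section 3.1, and Section 6.5 compares the arms with no common post-treatment cut-off

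*Combined protocol and SAP*

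**What the plan says.** The synopsis and Section 3.1 carry the same sentence: "Patients who are withdrawn from study treatment will be evaluated within 30 days and approximately 120 days after last study treatment". Neither limits it by arm. Section 4.6.1 reads: "After treatment discontinuation, patients will be asked to return to the clinic 120 days", with a margin of 30 days either way, again for both arms. Section 4.5 points to Appendix 1 for the schedule and adds: "All activities must be performed and documented for each patient". Footnote c of Appendix 1 repeats the general request to return and then says: "Only patients taking atezolizumab are required to return for the safety visit".

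On reporting, Section 5.3.1 collects all adverse events for 30 days after the last dose. Beyond that, "serious adverse events and adverse events of special interest will continue to be reported until 90 days after the last dose of study treatment". Both periods end sooner if new systemic anti-cancer therapy starts. The same section says: "Investigators will seek information on adverse events at each patient contact".

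On analysis, Section 6.5 says: "All adverse events occurring during or after the first study-drug dose will be summarized by treatment arm and NCI CTCAE grade". It also says: "Laboratory abnormalities will be summarized by treatment arm and grade". Neither sentence sets a limit on time since the last dose. The section leaves further detail to the SAP, and no such limit appears in the document reviewed.

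**The concern.** There are two problems. First, a site can read the control-arm visit as due (Section 3.1) or as not required (footnote c), so attendance in Arm B may depend on the site or on how the patient feels.

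Second, if footnote c is followed, one arm of an open-label study has an extra required look at examination and laboratory findings. The safety objective in Table 1 compares the two arms. An extra set of tests in one arm can only add detected abnormalities to that arm, so atezolizumab could look somewhat less safe than it is. With no cut-off in the tables, an excess caused by the drug could not be separated from one caused by the additional visit.

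**Working it through.** The plan gives no figure on this point, so there is none to reproduce. The check sets the schedule beside the reporting and analysis rules.

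**1. Timing of the visit (Section 4.6.1, footnote c).** 120 − 30 = day 90 and 120 + 30 = day 150. The visit falls at or after the end of the 90-day SAE/AESI window, so for those events it serves as a look back.

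**2. Required visits after the discontinuation visit (day 30 or earlier) and before study termination.**

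| Rule followed | Arm A | Arm B |
|---|---|---|
| Synopsis and Section 3.1 | 1 | 1 |
| Appendix 1, footnote c | 1 | 0 |

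**3. What is done at the visit (Appendix 1).** Nine rows are marked: limited examination, ECOG status, weight, hematology, chemistry, coagulation, thyroid tests, PSA (per standard of care), and survival and anti-cancer therapy follow-up. Four of these are safety laboratory panels.

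**4. Effect on laboratory tables under footnote c.** Take a man with k post-baseline hematology or chemistry sets during treatment. Both arms add 1 at the discontinuation visit, and Arm A adds 1 more:
- Arm A: k + 1 + 1 = k + 2 required sets.
- Arm B: k + 1 + 0 = k + 1.

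As the table reads, coagulation has no scheduled on-treatment test, so k = 0 and the count is 2 against 1. Nothing in footnote c excuses men who have started another therapy, so some of the extra Arm A samples may reflect the later drug. Section 6.5 would still count them.

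**5. Effect on adverse events under footnote c.**
- Events that are neither serious nor of special interest are collected only to day 30 in both arms. A visit at day 90 or later should add few of these.
- SAEs and AESIs starting from day 31 are in scope to day 90 at the latest: 90 − 30 = 60 days, and 60/90 = 67% of the longest possible window. The share is smaller for any man who starts new systemic therapy before day 90.
- Because events are elicited at patient contacts, Arm A has a required occasion to pick up this period and Arm B does not. Section 4.5.5 would keep some men who stop before progression on scheduled scans, but Appendix 1 footnote i ends on-study scans once treatment stops. Scans therefore cannot be relied on to even out the contacts.

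**6. Effect on efficacy.** Footnote d follows all patients for survival to study termination, so the OS comparison, its power and its alpha do not depend on this visit.

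**The case against.** The strongest reply is that the asymmetry is sensible and the textual conflict narrow. Footnote c can be read as asking all patients back and requiring only some. Section 4.6.1 also says asked, so it fits. Section 4.5 makes Appendix 1 the working schedule, footnotes included. Only the synopsis and Section 3.1 truly conflict. That stands.

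Control-arm men never received the antibody, most AESIs match its immune-mediated risks, and Section 3.4.4 gives weight to patient burden in this elderly population. Sparing them a clinic visit is defensible, especially in a study closing for futility (Section 3.3). That also stands, although the text does not give it as the reason.

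SAEs are hard to miss, and Section 5.4 requires them within 24 hours of the investigator learning of them in either arm. Section 5.6 keeps related late SAEs and AESIs reportable in both arms. Footnote d's survival follow-up may also bring control-arm contacts. This weakens the SAE part of the point. It does not touch the laboratory part, where a sample not taken cannot be reported.

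The SAP may yet set a cut-off, since Section 6.5 defers detail to it. If it does, the analysis half of the point is met.

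A reader might go further and infer that the arms have different reporting windows or duties. Section 5.3.1 gives them the same ones. A reader might also try to put a number on the false excess in Arm A. That needs the share of control-arm events missed without a visit, and the documents give nothing from which to derive it.

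**Conclusion.** The point holds as a minor one. The synopsis and Section 3.1 disagree with footnote c on who must attend. Under footnote c, Arm A has one required post-discontinuation visit with four safety laboratory panels and Arm B has none, while the between-arm tables have no common end point. The likely direction is against Arm A: mainly more late laboratory abnormalities and, to a lesser and unquantified extent, more SAEs or AESIs starting after day 30 and up to day 90 or new systemic therapy.

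This assumes that sites follow footnote c and that no cut-off is set elsewhere. The documents do not show when the footnote's last sentence was introduced or how many men are still to stop treatment, so its reach into data already collected is unknown.

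It would be a step too far to conclude that control-arm men must be given the clinic visit. A common cut-off restores a like-for-like comparison without it. It would also be wrong to read the point as a doubt about the primary endpoint.

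**What to change.** 1. **Align the text.** In the synopsis and Section 3.1, state that the 120-day visit is required of patients who received atezolizumab, as in footnote c. Section 4.6.1 can stay as it is.
2. **Set a common cut-off in Section 6.5 or the SAP.** Suggested wording: *Between-arm tables of laboratory abnormalities use samples taken up to 30 days after the last dose. SAEs and AESIs are tabulated separately by onset: up to day 30, and from day 31 to day 90 or the start of new systemic anti-cancer therapy, whichever is first.* Both arms have the discontinuation visit by day 30, so the laboratory tables then rest on the same schedule. Later Arm A samples can be listed for that arm alone, so no information is lost.
3. **Optional.** Telephone Arm B patients at about day 90 to ask about SAEs and AESIs.

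The cost is a wording edit in two places, one extra table split with no new data and, if step 3 is used, one call for each control-arm man who stops treatment after the change. No added control-arm clinic visit is needed.

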## Appendix 1 Schedule of Activities (cont.)

---

- f At screening, patients will be tested for HIV, HBsAg, HBsAb, total HBcAb, and HCV antibody. If a patient has a negative HBsAg test and a positive total HBcAb test at screening, an HBV DNA test should be performed. If a patient has a positive HCV antibody test at screening, an HCV RNA test must also be performed to determine if the patient has an active HCV infection.
- g Concomitant medications include any prescription medications or over-the-counter medications. At screening, any medications the patient has used within the 7 days prior to initiation of study treatment should be documented. At subsequent visits, changes to current medications or medications used since the last documentation of medications will be recorded.
- h At screening, any opiate analgesic medications a patient has used within the 7 days prior to initiation of study treatment should be documented.
- i Tumor assessments performed as standard of care prior to obtaining informed consent and within 28 days of Cycle 1, Day 1 may be used rather than repeating tests. All measurable and evaluable lesions should be assessed and documented at the screening visit. The same radiographic procedure must be used throughout the study for each patient. Results must be reviewed by the investigator before dosing at the next cycle. Tumor assessments will be performed at baseline, every 9 weeks (approximately every three cycles) following randomization for 27 weeks, and every 12 weeks thereafter, with additional scans as clinically indicated. Assessments will continue until confirmed radiographic disease progression per PCWG3 criteria. For patients who continue to receive study treatment following confirmed disease progression, assessments will continue until loss of clinical benefit. If an optional biopsy is to be performed at approximately the same time point of a tumor assessment or as a result of the radiographic determination (e.g., response or progression), samples should be acquired after all imaging scans have been performed, if at all possible. Once patients discontinue study treatment, tumor assessments should no longer be performed as per this study, and should be performed as per standard of care as determined by the investigator.
- j Complete physical examination includes evaluation of the head, eyes, ears, nose, and throat, and the cardiovascular, dermatological, musculoskeletal, respiratory, gastrointestinal, genitourinary, and neurological systems. Record abnormalities observed at baseline on the General Medical History and Baseline Conditions eCRF.
- k Perform a limited, symptom-directed examination at specified timepoints or as clinically indicated. Record new or worsened clinically significant abnormalities on the Adverse Event eCRF.
- l ECOG performance status, limited physical examination, and local laboratory assessments may be obtained  $\leq 4$  days before Day 1 of each cycle.
- m Vital signs include heart rate, respiratory rate, blood pressures, and temperature. Record abnormalities observed at baseline on the General Medical History and Baseline Conditions eCRF. Vital signs should be measured at every cycle for all patients. Vital signs should be measured within 60 minutes prior to each atezolizumab infusion and, if clinically indicated, during or after the infusion.
- n ECG recordings will be obtained as part of the screening assessment, at Day 1 of Cycle 4 and every 4 cycles thereafter during treatment, at the end of treatment visit, and when clinically indicated. ECGs will be reviewed by the investigator to determine patient eligibility at screening. Baseline evaluation of left ventricular ejection fraction should be considered for all patients, especially in those with cardiac risk factors and/or history of coronary artery disease. For patients with a history of clinically significant cardiac disease (including anatomic abnormality, coronary disease, congestive heart failure, abnormal LVEF, arrhythmia, or abnormal ECG) will be required to undergo a screening echocardiogram.

## Appendix 1 Schedule of Activities (cont.)

---

- ° Hematology consists of CBC, including RBC count, hemoglobin, hematocrit, WBC count with automated differential (neutrophils, lymphocytes, eosinophils, monocytes, basophils, and other cells), and platelet count. A manual differential can be done if clinically indicated. Absolute neutrophil count, lymphocyte count, platelet count, and hemoglobin for study inclusion-related tests must be obtained 14 days prior to initiation of study treatment.
- ° Serum chemistry includes BUN or urea, creatinine, sodium, potassium, magnesium, chloride, bicarbonate, calcium, phosphorus, glucose, total bilirubin, ALT, AST, alkaline phosphatase, lactate dehydrogenase, total protein, and albumin. In countries where serum bicarbonate is not considered a standard chemistry measurement (e.g., Japan), serum bicarbonate is not required as a laboratory study in the screening or on-study serum measurements. AST, ALT, bilirubin, creatinine, and albumin for study inclusion-related tests must be obtained 14 days prior to initiation of study treatment.
- ° Coagulation panel for study inclusion-related tests must be obtained 14 days prior to initiation of study treatment.
- ° TSH, free T3 (or total T3 for sites where free T3 is not performed), and free T4 will be assessed on Day 1 of Cycle 1 and every fourth cycle thereafter.
- ° At least two PSA samples (obtained at least 1 week apart) will be assessed locally at screening. Samples analyzed prior to screening do not have to be repeated. Historic values of PSA will be collected to calculate PSA velocity.
- ° The PSA sample will be assessed locally. PSA should be performed as per standard of care once patient discontinues study treatment.
- ° After signing the Informed Consent Form, retrieval and submission of archival tumor sample can occur more than 28 days prior to start of study treatment but must be submitted prior to enrollment. Tissue samples will not be collected for patients in the safety run-in phase. See Section 4.5.6 for tissue sample requirements.
- ° Tumor specimens are recommended at the time of confirmed radiographic disease progression per PCWG3 criteria, unless the location of the tumor renders the biopsy medically unsafe or infeasible per investigator decision. Biopsies should be performed within 40 days after progression or prior to the next anti-cancer therapy, whichever is sooner. See Section 4.5.6 for tissue sample requirements. Preferably, growing lesions should be selected.
- ° An SSE is defined as external beam radiation therapy to relieve skeletal symptoms (including initiation of radium-223 dichloride or other types of radionuclide therapy to treat symptoms of bone metastases), new symptomatic pathologic bone fracture, clinically apparent occurrence of spinal cord compression, or tumor related orthopedic surgical intervention
- ° The initial dose of atezolizumab will be delivered over 60 ( $\pm$  15) minutes. If the first infusion is tolerated without infusion-associated adverse events, the second infusion may be delivered over 30 ( $\pm$  10) minutes. If the 30-minute infusion is well tolerated, all subsequent infusions may be delivered over 30 ( $\pm$  10) minutes.
- ° Enzalutamide will be administered at a dose of 160 mg orally once daily. Study drug doses should be taken as close as possible to the same time each day. The study drug can be taken with or without food.

